13.2 On Treatment Specimen Collection

13.2.1 Every 12 weeks (3 months), all Cycles: Trial Treatment Administration

- Approximately up to 30 mL peripheral blood (serum for biomarkers)

13.2.2 At Week 9 **and** Week 18: Trial Treatment Administration

- Approximately up to 30 mL peripheral blood

13.3 Off-Treatment Specimen Collection (or at time of documented disease progression)

The following must be performed at the Off-Treatment visit (± 5 days):

- Approximately up to 30 mL peripheral blood (serum for biomarkers)
- Additional 7 mL peripheral blood, *only* if prior to Week 9 or Week 18

13.4 30 Days after Off Treatment Safety visit

The following must be performed at the EOT safety visit and should occur 30-days (+5 days) after the last dose of study treatment.

- Approximately up to 30 mL peripheral blood (serum for biomarkers)

13.5 Calendar of Specimen Collection for Correlative Studies

Timepoints	Tissue Sample	Peripheral Blood
Screening	X	X (Up to 30 mL)
Week 9		X (Up to 30 mL)
Every 12 weeks (3 months), all Cycles		X (Up to 30 mL)
Week 18		X (Up to 30 mL)
Off Treatment (or at time of documented disease progression)		X (Up to 30 mL) (plus additional 7mL, only if prior to Week 9 or 18)
30 Days after Off Treatment Safety Visit		X (Up to 30 mL)

14.0 MEASUREMENT OF EFFECT

14.1 Antitumor Effect in Solid Tumors

For the purposes of this study, patients should be re-evaluated for response every 9 weeks (\pm 9 days) which corresponds to the 3 week cycles of therapy. In addition to a baseline scan, confirmatory scans should also be obtained \geq 4 weeks following initial documentation of objective response. (*Note: Lesions are either measurable or non-measurable using the criteria provided below. The term “evaluable” in reference to measurability will not be used because it does not provide additional meaning or accuracy.*)

Response and progression will be evaluated in this study using the international criteria proposed by the revised Response Evaluation Criteria in Solid Tumors (RECIST) version 1.1 guideline(s). Changes in the largest diameter (unidimensional measurement) of the tumor lesions and the shortest diameter in the case of malignant lymph nodes are used in RECIST.

The following general principles must be followed:

1. To assess objective response, it is necessary to estimate the overall tumor burden at baseline to which subsequent measurements will be compared. All baseline evaluations should be performed as closely as possible to the beginning of treatment and never more than four weeks before registration.
2. Measurable disease is defined by the presence of at least one measurable lesion.
3. All measurements should be recorded in metric notation by use of a ruler or calipers.
4. The same method of assessment and the same technique must be used to characterize each identified lesion at baseline and during follow-up.

14.2 Definitions

Evaluable for Objective Response

Only those patients who have measurable disease present at baseline, have received at least one cycle of therapy, and have had their disease re-evaluated will be considered evaluable for response. These patients will have their response classified according to the definitions stated below. (*Note: Patients who exhibit objective disease progression prior to the end of cycle 1 will also be considered evaluable.*)

Evaluable Non-Target Disease Response

Patients who have lesions present at baseline that are evaluable but do not meet the definitions of measurable disease, have received at least one cycle of therapy, and have had their disease re-evaluated will be considered evaluable for non-target disease. The response assessment is based on the presence, absence, or unequivocal progression of the lesions.

14.3 Disease Parameters

Measurable Disease

Measurable lesions are defined as those that can be accurately measured in at least one dimension (longest diameter to be recorded) as ≥ 20 mm by chest x-ray, as ≥ 10 mm with CT scan, or ≥ 10 mm with calipers by clinical exam. All tumor measurements must be recorded in millimeters.

NOTE: Tumor lesions that are situated in a previously irradiated area may be considered measurable if they have grown subsequent to previous radiation.

Malignant Lymph Nodes

To be considered pathologically enlarged and measurable, a lymph node must be ≥ 15 mm in **short** axis when assessed by CT scan (CT scan slice thickness recommended to be no greater than 5 mm). At baseline and in follow-up, only the **short** axis will be measured and followed.

Non-measurable Disease

All other lesions (or sites of disease), including small lesions (longest diameter < 10 mm or pathological lymph nodes with ≥ 10 to < 15 mm short axis), are considered non-measurable disease. Bone lesions, leptomeningeal disease, ascites, pleural/pericardial effusions, lymphangitis cutis/pulmonitis, inflammatory breast disease, and abdominal masses (not followed by CT or MRI), are considered as non-measurable.

NOTE: Cystic lesions that meet the criteria for radiographically defined simple cysts should not be considered as malignant lesions (neither measurable nor non-measurable) since they are, by definition, simple cysts.

‘Cystic lesions’ thought to represent cystic metastases can be considered as measurable lesions, if they meet the definition of measurability described above. However, if non-cystic lesions are present in the same patient, these are preferred for selection as target lesions.

Target Lesions

All measurable lesions up to a maximum of 2 lesions per organ and 5 lesions in total, representative of all involved organs, should be identified as **target lesions** and recorded and measured at baseline. Target lesions should be selected on the basis of their size (lesions with the longest diameter), be representative of all involved organs, but in addition should be those that lend themselves to reproducible repeated measurements. It may be the case that, on occasion, the largest lesion does not lend itself to reproducible measurement in which circumstance the next largest lesion which can be measured

reproducibly should be selected.

A sum of the diameters (longest for non-nodal lesions, short axis for nodal lesions) for all target lesions will be calculated and reported as the baseline sum diameters. If lymph nodes are to be included in the sum, then only the short axis is added into the sum. The baseline sum of the diameters will be used as reference to further characterize any objective tumor regression in the measurable dimension of the disease.

Non-target Lesions

All other lesions (or sites of disease) including any measurable lesions over and above the 5 target lesions should be identified as **non-target lesions** and should also be recorded at baseline. Measurements of these lesions are not required, but the presence or absence of unequivocal progression of each should be noted throughout follow-up.

14.4 **Methods for Evaluation of Disease**

All measurements should be taken and recorded in metric notation using a ruler or calipers. All baseline evaluations should be performed as closely as possible to the beginning of treatment and never more than 4 weeks (28 days) before the beginning of treatment.

The same method of assessment and the same technique must be used to characterize each identified and reported lesion at baseline and during follow-up. Imaging-based evaluation is preferred to evaluation by clinical examination unless the lesion(s) being followed cannot be imaged but are assessable by clinical exam.

Clinical Lesions

Clinical lesions will only be considered measurable when they are superficial (e.g., skin nodules and palpable lymph nodes) and ≥ 10 mm in diameter as assessed using calipers (e.g., skin nodules). In the case of skin lesions, documentation by color photography, including a ruler to estimate the size of the lesion, is recommended.

Chest X-ray

Lesions on chest x-ray are acceptable as measurable lesions when they are clearly defined and surrounded by aerated lung. However, CT is preferable.

Conventional CT and MRI

This guideline has defined measurability of lesions on CT scan based on the assumption that CT slice thickness is 5 mm or less. If CT scans have slice thickness greater than 5 mm, the minimum size for a measurable lesion should be twice the slice thickness. MRI is also acceptable in certain situations (e.g. for body scans).

Use of MRI remains a complex issue. MRI has excellent contrast, spatial, and temporal

resolution; however, there are many image acquisition variables involved in MRI which greatly impact image quality, lesion conspicuity, and measurement. Furthermore, the availability of MRI is variable globally. As with CT, if an MRI is performed, the technical specifications of the scanning sequences used should be optimized for the evaluation of the type and site of disease. Furthermore, as with CT, the modality used at follow-up must be the same as was used at baseline and the lesions should be measured/assessed on the same pulse sequence. It is beyond the scope of the RECIST guidelines to prescribe specific MRI pulse sequence parameters for all scanners, body parts, and diseases. Ideally, the same type of scanner should be used and the image acquisition protocol should be followed as closely as possible to prior scans. Body scans should be performed with breath-hold scanning techniques, if possible.

Ultrasound

Ultrasound is not useful in assessment of lesion size and should not be used as a method of measurement. Ultrasound examinations cannot be reproduced in their entirety for independent review at a later date and, because they are operator dependent, it cannot be guaranteed that the same technique and measurements will be taken from one assessment to the next. If new lesions are identified by ultrasound in the course of the study, confirmation by CT or MRI is advised. If there is concern about radiation exposure at CT, MRI may be used instead of CT in selected instances.

Endoscopy, Laparoscopy

The utilization of these techniques for objective tumor evaluation is not advised. However, such techniques may be useful to confirm complete pathological response when biopsies are obtained or to determine relapse in trials where recurrence following complete response (CR) or surgical resection is an endpoint.

Tumor markers

Tumor markers alone cannot be used to assess response. If markers are initially above the upper normal limit, they must normalize for a patient to be considered in complete clinical response. Specific guidelines for both CA-125 response (in recurrent ovarian cancer) and PSA response (in recurrent prostate cancer) have been published [JNCI 96:487-488, 2004; J Clin Oncol 17, 3461-3467, 1999; J Clin Oncol 26:1148-1159, 2008]. In addition, the Gynecologic Cancer Intergroup has developed CA-125 progression criteria which are to be integrated with objective tumor assessment for use in first-line trials in ovarian cancer [JNCI 92:1534-1535, 2000].

Cytology, Histology

These techniques can be used to differentiate between partial responses (PR) and complete responses (CR) in rare cases (e.g., residual lesions in tumor types, such as germ cell tumors, where known residual benign tumors can remain).

The cytological confirmation of the neoplastic origin of any effusion that appears or worsens during treatment when the measurable tumor has met criteria for response or

stable disease is mandatory to differentiate between response or stable disease (an effusion may be a side effect of the treatment) and progressive disease.

14.5 Response Criteria

14.5.1 Evaluation of Target Lesions

Complete Response (CR)

Disappearance of all target lesions. Any pathological lymph nodes (whether target or non-target) must have reduction in short axis to < 10 mm.

Partial Response (PR)

At least a 30% decrease in the sum of the diameters of target lesions, taking as reference the baseline sum diameters

Progressive Disease (PD)

At least a 20% increase in the sum of the diameters of target lesions, taking as reference the smallest sum on study (this includes the baseline sum if that is the smallest on study). In addition to the relative increase of 20%, the sum must also demonstrate an absolute increase of at least 5 mm. (**NOTE:** the appearance of one or more new lesions is also considered progression).

Stable Disease (SD)

Neither sufficient shrinkage to qualify for PR nor sufficient increase to qualify for PD, taking as reference the smallest sum diameters while on study.

14.5.2 Evaluation of Non-Target Lesions

Complete Response (CR)

Disappearance of all non-target lesions. All lymph nodes must be non-pathological in size (<10 mm short axis). Note: If tumor markers are initially above the ULN, they must normalize for a patient to be considered in complete CR.

Non-CR/Non-PD

Persistence of one or more non-target lesion(s) and/or maintenance of tumor marker level above the normal limits.

Progressive Disease (PD)

Appearance of one or more new lesions and/or *unequivocal progression* of existing non-target lesions. *Unequivocal progression* should not normally trump target lesion status. It must be representative of overall disease status change, not a single lesion increase.

When the patient also has measurable disease, there must be an overall level of substantial worsening in non-target disease such that, even in the presence of SD or PR

in target disease, the overall tumor burden has increased sufficiently to merit discontinuation of therapy. A modest “increase” in the size of one or more non-target lesions is usually not sufficient to qualify for unequivocal progression status. The designation of overall progression solely on the basis of change in non-target disease in the face of SD or PR of target disease will therefore be extremely rare.

When the patient only has non-measurable disease, the increase in overall disease burden should be comparable in magnitude to the increase that would be required to declare PD for measurable disease: i.e., an increase in tumor burden from “trace” to “large”, an increase in nodal disease from “localized” to “widespread”, or an increase sufficient to require a change in therapy.

Although a clear progression of “non-target” lesions only is exceptional, the opinion of the treating physician should prevail in such circumstances, and the progression status should be confirmed at a later time by the review panel (or Principal Investigator).

14.5.3 Evaluation of New Lesions

The appearance of new lesions constitutes Progressive Disease (PD).

A growing lymph node that did not meet the criteria for reporting as a measurable or non-measurable lymph node at baseline should only be reported as a new lesion (and therefore progressive disease) if it:

- a) increases in size to ≥ 15 mm in the short axis or;
- b) there is new pathological confirmation that it is disease (regardless of size).

14.5.4 Evaluation of Best Overall Response

The best overall response is the best response recorded from the start of the treatment until disease progression/recurrence or non-protocol therapy (taking as reference for progressive disease the smallest measurements recorded since the treatment started). The patient’s best response assignment will depend on the achievement of measurement criteria.

Target Lesions	Non-Target Lesions	New Lesions*	Best Overall Response	Remarks
CR	CR	No	CR	Confirm by repeat assessments ≥ 4 weeks after criteria for response are first met.
CR	Non-CR/Non-PD***	No	PR	
CR	Not evaluated	No	PR	
PR	Non-PD***/not evaluated	No	PR	

SD	Non-PD ^{***} /not evaluated	No	SD	Follow-up assessments must have met SD criteria at least once ≥8 weeks from study entry.
PD	Any	Yes or No	PD	
Any	PD ^{**}	Yes or No	PD ^{***}	
Any	Any	Yes	PD	No prior SD, PR or CR

* See RECIST 1.1 manuscript for further details on what is evidence of a new lesion.
 
** In exceptional circumstances, unequivocal progression in non-target lesions may be accepted as disease progression.
 
*** PD in non-target lesions should not normally trump target lesion status. It must be representative of overall disease status change, not a single lesion increase. Please refer to the Evaluation of Non-Target Lesions – Progressive Disease section for further explanation.
 
 • Patients with a global deterioration of health status requiring discontinuation of treatment without objective evidence of disease progression at that time should be reported as “symptomatic deterioration.” Every effort should be made to document the objective progression even after discontinuation of treatment. • In some circumstances, it may be difficult to distinguish residual disease from normal tissue. When the evaluation of CR depends on this determination, it is recommended that the residual lesion be investigated (fine needle aspirate/biopsy) before confirming the CR status. 				

14.5.5 Duration of Response

Duration of Overall Response

The duration of overall response is measured from the time measurement criteria are met for CR or PR (whichever is first recorded) until the first date that recurrent or progressive disease is objectively documented (taking as reference for progressive disease the smallest measurements recorded since the treatment started).

The duration of overall CR is measured from the time measurement criteria are first met for CR until the first date that progressive disease is objectively documented.

Duration of Stable Disease

Stable disease is measured from the start of the treatment until the criteria for progression are met, taking as reference the smallest measurements recorded since the treatment started, including the baseline measurements.

14.6 Disease Control Rate (DCR)

DCR is the proportion of patients whose best overall response per RECIST criteria is complete response (CR), partial response (PR), or stable disease (SD). Disease control must be confirmed by repeat assessments performed at an interval of no less than 4 weeks for CR and PR. For SD, disease control must be confirmed by repeat assessments performed at an interval of no less than 8 weeks.

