At the 2015 ASCO, the preliminary results of a Phase I-II trial of PD1 (nivolumab) in advanced HCC was reported (19). Patients received nivolumab 0.1- 10 mg/kg intravenously for up to two years. The study enrolled 41 patients. Eighteen patients remained on the study and 23 discontinued treatment due to progressive disease (n=17), complete response (n=2), drug-related adverse events (AEs, n=2) and non-drug-related AEs (n=2). Drug-related AEs of any grade occurred in 29 patients (71%, 17% grade 3 or 4) with >10% of patients experiencing aspartate aminotransferase (AST) increase and rash (each 17%), alanine aminotransferase (ALT) and lipase increase (each 15%) and amylase increase (12%). Grade 3 and 4 AEs >5% were AST increase (12%), ALT increase (10%) and lipase increase (5%). A dose-limiting toxicity occurred in one patient at 10 mg/kg; no maximum tolerated dose was defined in any cohort. Response was evaluable in 39 patients: 2 CR (5%) and 7 partial response (PR 18%). Response duration was 14-17+ months for CR, <1-8 months for PR and 1.5-17+ months for stable disease. Overall survival rate at 6 months is 72%. The conclusions were that nivolumab had manageable AE profile and produced durable responses across all dose levels and HCC cohorts (no active hepatitis virus infection or virus-infected HCC), with a favorable 6-month overall survival rate.

The promising results with the tremelimumab and nivolumab trials suggest that further evaluation of immunotherapy in HCC is indicated. These also provide a rational basis to conduct further investigation into this approach.

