16.0 STATISTICAL CONSIDERATIONS

16.1 Objectives and Endpoints

This is a single-arm phase II trial of Pembrolizumab (Keytruda®) in patients with advanced, unresectable hepatocellular carcinoma. The primary objective is to assess its therapeutic efficacy in patients with unresectable hepatocellular carcinoma (HCC). The

primary endpoint is disease-control rate (DCR) defined as the proportion of patients achieving a best overall response of either a CR, PR or SD (that is maintained for at least 8 weeks).

Secondary endpoints include progression-free survival (PFS), overall survival (OS), objective response rate (ORR), duration of response (DOR), and toxicity profile of Pembrolizumab. We will also evaluate the expression levels of PD-L1 in tumor tissue, as well as serum titers of hepatitis B or C in patients with hepatitis B or C, respectively, for whom specimens are available.

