16.2 Study Design and Sample Size Justification

The primary endpoint for this single arm phase II trial is disease control rate (CR, PR, or SD). The rationale for using disease control rate (DCR) as the primary endpoint is derived from the clinical experience with Sorafenib (SHARP trial 2008), which was approved as the first and only therapeutic agent definitively proven to prolong survival in patients with advanced HCC. The disease control rate of Sorafenib was 43% in the SHARP trial [7]. We hypothesize that Pembrolizumab will achieve a similar or higher disease control rate. We set a null hypothesis rate of 18% disease control, since standard chemotherapy regimens generally result in a DCR of 15-20%.

We propose study size based on the Simon 2-stage MiniMax design [39] with a one-sided significance level of 5% and 90% power. Assuming that Pembrolizumab therapy will not be of further interest if DCR were no better than 18% (null hypothesis) while a rate of 43% would merit further investigation, the Simon MiniMax design requires at most 28 patients: 14 patients to be enrolled in the first stage and possibly an additional 14 in the second stage. If no more than 2 of the 14 patients in stage 1 achieve CR/PR/SD, the trial will stop and Pembrolizumab will be considered ineffective. If 3 or more of the stage 1 patients achieve CR/PR/SD, our study will continue to a second stage and enroll an additional 14 patients for a total of 28. If 9 or more out of 28 study patients achieve CR/PR/SD, we will report an observed DCR of at least 32% and conclude that the true DCR significantly exceeds a null rate of 18%. With this design, the chance of early stopping at the end of stage 1 is 53% if the null hypothesis of 18% DCR is true, whereas there is a very small chance, 2%, of early termination if the true DCR is 43%.

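### The plan gives conflicting rules on whether a CR or PR must be confirmed to count as disease control, and never says how an unconfirmed CR or PR is classed

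*Combined protocol and SAP*

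**What the plan says.** The documents define DCR in several places, and the definitions differ.

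- **Section 14.6:** "Disease control must be confirmed by repeat assessments performed at an interval of no less than 4 weeks for CR and PR". Its next sentence requires SD, too, to be confirmed by repeat assessments, at least 8 weeks apart.
- **Abbreviations table:** DCR counts confirmed responses.
- **Sections 3.1 and 16.1:** DCR rests on best overall response, in 16.1 as "a best overall response of either a CR, PR or SD (that is maintained for at least 8 weeks"). Neither asks for a CR or PR to be confirmed, and nor does 16.2.
- **Section 17.2.3 (interim analysis):** refers to 14.5 for the response rule, not to 14.6.
- **Section 14.5.4:** for SD, "Follow-up assessments must have met SD criteria at least once ≥8 weeks from study entry". Its table also carries a remark that response be confirmed at 4 weeks or more, with no statement of what follows if it is not.
- **Section 14.5.1:** SD is "Neither sufficient shrinkage to qualify for PR nor sufficient increase to qualify for PD", so a scan that meets PR is not an SD scan.

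Section 14.1 schedules scans every 9 weeks (±9 days), with a further scan at least 4 weeks after a first response.

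**The concern.** A patient whose best scan is a PR that is never confirmed can be a success or a failure on the primary endpoint, depending on which section the analyst applies. Where confirmation is required and there is no fallback to SD, a patient whose tumour shrank more can be ranked below one whose tumour did not shrink, although both progressed on the same date.

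Confirmation has a purpose for ORR, where the depth of response is the endpoint. For DCR the three categories count the same, so the requirement adds no information and can only take patients out of the numerator. The decision rules are tight: 3 of 14 to continue, 9 of 28 to succeed. One reclassified patient is the difference between 8/28 and 9/28.

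**Working it through.** **1. The plan's design figures.** Inputs from 16.2: "one-sided significance level of 5% and 90% power"; DCR "no better than 18% (null hypothesis) while a rate of 43% would merit further investigation"; stop "If no more than 2 of the 14 patients in stage 1 achieve CR/PR/SD"; succeed with 9 or more of 28.

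P(stop at stage 1) = P(X₁ ≤ 2), with X₁ ~ Bin(14, p).
P(success) = Σ over x = 3 to 14 of P(X₁ = x) · P(X₂ ≥ 9 − x), with X₂ ~ Bin(14, p).

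- p = 0.18: early stopping 0.526, type I error 0.0495.
- p = 0.43: early stopping 0.024, power 0.905.

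These agree with the stated 53%, 2%, 5% and 90%. The design itself is sound.

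**2. The definitions applied to scan sequences on the 9-week schedule.** Every PR below is unconfirmed.

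| Sequence | 14.6 read literally | 14.6 for CR/PR, 14.5.4 for SD | 3.1 / 16.1 |
|---|---|---|---|
| PR wk 9, PD by wk 18 | not counted | not counted | counted |
| SD wk 9, PD wk 18 | not counted (SD not repeated) | counted, if the scan is on day 56 or later | counted, if the 8 weeks run from treatment start |
| SD wk 9, PR wk 18, PD by wk 27 | not counted | SD criterion met at wk 9, if on day 56 or later | counted |
| SD wk 9, SD wk 18, PD wk 27 | counted (SD repeated 9 weeks apart) | counted | counted |

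Under literal 14.6 the inversion is between the third and fourth rows. With SD judged by 14.5.4 it is between the first and second. Each way of judging SD within section 14 therefore produces one inversion, in a different place.

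The day-56 condition arises because 8 weeks is 56 days, while the week-9 scan may fall as early as 63 − 9 = 54 days.

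**3. Size, as a sensitivity range.** The documents give no proportion of unconfirmed responses. Assume a response rate of 15% to 23% (the upper value is 9/39 in the nivolumab trial cited in 1.1) and that 10% to 20% of responses are unconfirmed and lost.

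- Smallest loss: 0.15 × 0.10 = 0.015. DCR 0.43 − 0.015 = 0.415, power 0.876.
- One in seven lost at 23%: 0.23/7 = 0.033. DCR 0.397, power 0.833.
- Largest loss: 0.23 × 0.20 = 0.046. DCR 0.384, power 0.796.

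In 28 patients this is 28 × 0.015 = 0.4 to 28 × 0.046 = 1.3 patients.

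Under the null the same mechanism lowers the rejection probability. A loss of 1 point from 18% gives 0.036, and a loss of 5 points gives 0.007, against 0.0495.

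**The case against.** The strongest reply is that 14.6 treats SD no more leniently than PR. A reader might infer that a patient with PR at week 9 and then progression always fails while a patient with SD at week 9 and the same progression date always succeeds. The documents do not support that. On the literal text of 14.6 both fail, because the SD is not repeated either. The contrast at week 9 appears only when SD is judged by 14.5.4. This reply stands for the week-9 pair, but it does not remove the inversion at week 18.

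A reader might also infer that an unconfirmed PR must be scored as PD. That does not follow. Section 14.5.4 takes the best response recorded up to progression, and a remark in its PD rows refers to there being no earlier SD, PR or CR. The extraction does not show how many rows that remark covers. The case is unresolved and may lean towards PR; it is not settled as a failure. Likewise, failure on the primary endpoint cannot be stated outright, since 3.1 and 16.1 would count the patient.

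Harm at stage 1 is not established. Section 17.2.3 suspends accrual and sets no data cut-off, so nothing prevents waiting for the confirming scan.

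The power figures can be challenged too. The nivolumab result, "Response duration was 14-17+ months for CR, <1-8 months for PR", makes short responses plausible, but the lower end of a range from preliminary data does not show that any PR was unconfirmed. If SD is judged by 14.5.4, an unconfirmed PR with an SD scan at 8 weeks or later is not lost, which pulls towards the small end of the range. The documents also do not say whether the 18% and 43% reference rates required confirmation.

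**Conclusion.** The conflict is real and concerns the primary endpoint. Section 14.6 and the abbreviations require confirmation of CR and PR; 3.1, 16.1 and 16.2 do not; 17.2.3 points elsewhere; and nothing classes an unconfirmed CR or PR. Under 14.6 alone, SD–PR–PD ranks below SD–SD–PD on the same dates. With SD judged by 14.5.4, PR–PD ranks below SD–PD, provided the week-9 scan falls on day 56 or later.

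Any loss is conservative for type I error. Its cost is power: from 0.905 to between 0.88 and 0.80 if 1.5 to 4.6 points of DCR are lost. That range rests on the assumed response rate and unconfirmed share, and on the 43% benchmark not having required confirmation. It is not an estimate of what will happen in this trial. The reason to act is that a single patient can decide the trial and the text does not say how to score that patient.

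**What to change.** State one DCR rule and use it in 3.1, 14.5.4, 14.6, 16.1, 16.2, 17.2.3 and the abbreviations table. Suggested content: a CR or PR documented at least 8 weeks after a single named start date, but not confirmed, is classed as SD for DCR and counts as disease control. Confirmation is required only for ORR and duration of response.

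In the same edit:

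- reconcile the SD sentence of 14.6 (repeat assessments at least 8 weeks apart) with 14.5.4 (criterion met once, at least 8 weeks from study entry);
- name the date from which the 8 weeks run, bearing in mind that scans are timed from enrollment and the window allows day 54;
- remove the confirmation wording from the DCR entry in the abbreviations, and add it to ORR in 14.7 so that it matches 3.2.

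The cost is coordinated wording changes in several sections. No new scans or data are needed. With the fallback in place no disease-control patient is lost on this ground, and the design keeps power 0.905 and type I error 0.0495.
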